#### Proportion of patients with clinical benefit in the Extension Phase

Proportion of patients with clinical benefit is defined by the number of patients with clinical benefit as assessed by investigator during Extension Phase (begins after the end of the Core Phase) divided by the number of patients in the Extension Phase.

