4.3 Definition of end of study

Study recruitment will stop when approximately 3,000 patients are enrolled.

The planned overall study duration of the Core Phase will be from FPFV to 18 months after LPFV. At the time of Core Phase end if patients are still deriving clinical benefit and ribociclib is not approved or available and reimbursed, patients may be transitioned to the Extension Phase trial period and continue to receive the drugs until progression, intolerance, death or physician/patient decision, but only safety and clinical benefit as assessed by investigator will be collected during the Extension Phase.

The duration of the Extension Phase will be 18 months from LPLV of the Core Phase. During the Extension Phase, if ribociclib is approved and reimbursed, patients will be transitioned to prescription or drug access/support program(s) according to local laws and regulations.

The study will end after completion of the Extension Phase and all remaining patients will discontinue from the study. Patients who complete the Extension Phase, and continue to derive clinical benefit from the treatment based on the investigator's evaluation will receive ribociclib from prescription (if approved and reimbursed), another Post-Trial Access (PTA) program, or other drug access/support program(s).

Post-Trial Access (PTA) means the provision of treatment to trial participants following their completion of trial participation. PTA will be provided until one of the following is met: patient no longer derives clinical benefit, investigator discontinues treatment, launch or reimbursement (where applicable), treatment fails to achieve registration in the trial participant's country, or the clinical program is discontinued for any other reason.

The mechanism of PTA for this Extension Phase is provision of the Novartis investigational product in a non-trial setting (known as post-study drug supply [PSDS]) when no further safety or efficacy data are required, or any other mechanism appropriate for the country.

This PTA mechanism must comply with local laws and regulations in the participating trial countries. If Novartis discontinues the PSDS for this trial, Novartis will work with investigators to transition patients onto locally available alternative treatment, or standard of care.

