## 2.1.2 General analysis conventions

**Pooling of centers:** Unless specified otherwise, data from all study centers will be pooled for the analysis. Protocol deviations, number of patients in analysis populations and discontinuations from study treatment will be summarized by center.

**Qualitative data** (e.g., gender, race, etc.) will be summarized by means of contingency tables; a missing category will be included as applicable. Percentages will be calculated using the number of patients in the relevant population or subgroup as the denominator.

**Quantitative data** (e.g., age, body weight, etc.) will be summarized by appropriate descriptive statistics (i.e. mean, standard deviation, median, minimum, and maximum).

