#### 2.2.4 Safety Set in Extension Phase

The Safety set in the Extension Phase includes all patients who received at least one dose of study medication defined as ribociclib, or letrozole, or goserelin, or leuprolide in the Extension Phase

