#### Proportion of patients with clinical benefit in the Extension Phase

Proportion of patients with clinical benefit as assessed by the investigator will be summarized at scheduled visits. Clinical benefit will be summarized using the Safety Set in Extension Phase.

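### The by-visit Extension Phase clinical-benefit percentage has a fixed denominator, so patients who move to prescription or access supply while still benefiting lower it, and no rule handles them

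*SAP*

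**What the plan says.** SAP 2.7.1 gives the numerator as "the number of patients with clinical benefit as assessed by investigator during Extension Phase" and the denominator by the words "divided by the number of patients in the Extension Phase". SAP 2.7.2 then sets the timing and the analysis set: "Proportion of patients with clinical benefit as assessed by the investigator will be summarized at scheduled visits", and "Clinical benefit will be summarized using the Safety Set in Extension Phase". Protocol 10.5.1 and SAP 1.2.2 also call for reporting at each scheduled visit.

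The set is defined once for the whole phase in SAP 2.2.4: "The Safety set in the Extension Phase includes all patients who received at least one dose of study medication" in that phase. SAP 2.1.2 fixes the base for categorical tables: "Percentages will be calculated using the number of patients in the relevant population or subgroup as the denominator". It adds that "a missing category will be included as applicable".

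Protocol 4.3 provides an exit that does not depend on benefit: "During the Extension Phase, if ribociclib is approved and reimbursed, patients will be transitioned to prescription or drug access/support program(s"; the sentence goes on to refer to local law. Protocol 7.1.5 repeats the rule. Under Protocol 7.2.1 the investigator confirms benefit at three-monthly study visits.

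SAP 2.7.3, on missing values, censoring and discontinuations, deals only with time to progression.

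**The concern.** A percentage reported visit by visit invites the reader to take a decline as patients losing benefit. Here it can also decline because ribociclib became reimbursed in a patient's country. Such a patient remains in the Safety Set in Extension Phase but has no later study visit at which benefit could be confirmed. The SAP does not exclude that patient, carry the last status forward, censor at the move or show the move as its own category.

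This is the only efficacy endpoint of the Extension Phase (Protocol Table 3-1, SAP Table 1-1), and SAP 1.1 plans a separate study report for that phase. The gap may come from timing. The SAP states that it is based on protocol version 02, and the last entry in its document history is dated 18 December 2019. Protocol Amendment 04, which defined the Extension duration and the transition plan, is dated 23 January 2020. The list in SAP 1.1 of reasons for which Extension treatment ends does not include transition to other supply.

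**Working it through.** The documents give no figure for this endpoint, so there is nothing to reproduce. The check is proportion arithmetic.

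**Inputs**
- N = 415 patients transitioned to the Extension Phase (Protocol, Amendment 04 rationale), taken as the size of the Safety Set in Extension Phase.
- T = patients already moved to prescription or access supply by a given visit. Not given; assumed to be 0% to 75% of N.
- q = share of the N − T patients not moved who no longer benefit, including those who stopped for progression, toxicity or death. Not given; assumed to be 15%, with 5% and 30% as alternatives.
- B = patients with benefit confirmed at the visit = (N − T) × (1 − q), rounded to whole patients.

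**Formulas**
- SAP rule: B / N.
- Excluding only moved patients: r = B / (N − T).
- Since B / N = r × (1 − T/N), the SAP figure lies below r by r × T/N.

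**Worked case, 25% moved, q = 15%**
- T = 0.25 × 415 = 103.75, rounded to 104; N − T = 311.
- Without benefit: 0.15 × 311 = 46.65, rounded to 47; B = 311 − 47 = 264.
- SAP rule: 264/415 = 63.6%.
- Excluding moved patients: 264/311 = 84.9%.
- Gap: 0.849 × 104/415 = 21.3 percentage points, which matches 84.9 − 63.6.
- Counting moved patients as benefiting at exit: (264 + 104)/415 = 368/415 = 88.7%.

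**Varying the share moved, q = 15%**

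| Moved | T | B | SAP rule B/415 | B/(415 − T) |
|---|---|---|---|---|
| 0% | 0 | 353 | 85.1% | 85.1% |
| 10% | 42 | 317 | 76.4% | 85.0% |
| 25% | 104 | 264 | 63.6% | 84.9% |
| 50% | 208 | 176 | 42.4% | 85.0% |
| 75% | 311 | 88 | 21.2% | 84.6% |

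**Varying q, 25% moved**
- q = 5%: 295/415 = 71.1% against 295/311 = 94.9%.
- q = 30%: 218/415 = 52.5% against 218/311 = 70.1%.

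**No loss of benefit at all (q = 0)**
- 25% moved: 311/415 = 74.9%.
- 50% moved: 207/415 = 49.9%.

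The last case isolates the problem: the reported percentage halves although no patient has lost benefit.

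**The case against.** **The SAP never says that moved patients count as having no benefit.** A reader might infer from the formula that they are classified so, but no text does this. They may appear in a missing category under SAP 2.1.2. That stands. It does not protect the percentage, because the same section keeps the whole population as the base.

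**Other readings of the denominator exist.** Patients in the Extension Phase at a visit could mean those still in it. SAP 2.7.2 names the Safety Set in Extension Phase, however, and SAP 2.2.4 defines that set by one dose at any time in the phase, so the fixed base is the better-supported reading. The alternatives do not rescue the endpoint. Among patients still on treatment the figure would be near 100% by design, since Protocol 7.2.1 ties continued treatment to confirmed benefit. Read as benefit at any time in the phase, it would also be near 100%, since Protocol 4.1 admits patients who are still benefiting.

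**The percentage does not simply track reimbursement.** A reader might infer that it measures reimbursement timing and nothing else. The documents do not support that: patients also leave for progression, intolerance, death or a physician or patient decision, and many of those exits are real loss of benefit. The figure mixes the two causes.

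**Disposition is reported.** SAP 2.3.6 tabulates patients still on treatment, patients discontinued and the primary reason, on the same set. This helps, but the tables are not by visit, and the withdrawal reasons in Protocol 7.1.5 contain no entry for transition to other supply.

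**The endpoint is secondary and descriptive.** No hypothesis is tested. This limits the consequence to interpretation.

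**Conclusion.** The point holds. Followed as written, SAP 2.7.1 and 2.7.2 give a by-visit percentage that falls when patients transition while still benefiting, and nothing in the SAP separates that fall from loss of benefit. The size is the share moved times the benefit rate among patients not moved: about 21 percentage points (85% to 64%) if 25% have moved and 85% of the rest benefit. Both shares are assumptions. The documents fix only the 415 and the direction, so the actual effect could be negligible or large. It applies to visits after the move and rests on reading the Safety Set in Extension Phase as the denominator at every visit. It does not show that the SAP declares these patients to be without benefit, or that the measure carries no information on benefit. No error rate is affected.

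**What to change.** - **By-visit table.** Keep the full Safety Set in Extension Phase and show mutually exclusive categories at each visit: benefit confirmed; transitioned to commercial or access supply while benefiting; stopped for progression, toxicity or death; stopped for other reasons; missing.
- **Time-to-event summary.** Add a Kaplan-Meier time to loss of clinical benefit. The event is progression, death from the disease or investigator-declared loss of benefit, censored at transition. This assumes that the timing of approval and reimbursement is unrelated to a patient's prognosis. The SAP should also state how stops for toxicity and deaths from other causes are handled.
- **If a single proportion is kept.** Remove only the transitioned patients from the denominator and retain those who stopped without benefit. Do not restrict it to patients still on treatment, because true loss of benefit would then drop out of the figure.
- **SAP 2.7.3.** Add a sentence stating the rule for transitioned patients.

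The cost is SAP wording and a little more analysis, on one condition. The sponsor must confirm that transitions, and benefit status at transition, can be identified from the End of Extension Treatment page or its free text, since Protocol 7.1.5 lists no such reason.

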#### 2.7.2 Statistical hypothesis, model, and method of analysis

#### TTP

Time to progression data will be listed and summarize. The distribution of time to progression will be estimated using the Kaplan-Meier method and the median time to progression will be presented along with 95% confidence interval (Brookmeyer and Crowley 1982) only if a sufficient number of responses are observed. The results will be plotted graphically. The 25th and 75th percentiles and Kaplan-Meier estimated probabilities with corresponding 95% CIs (Brookmeyer and Crowley 1982) at several time points (including at least 3, 6, 9, 12, 15, 18, 24 and 30 months).

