10.5 Secondary objectives

10.5.1 Secondary objective(s)

The secondary objective of this study is to assess the clinical efficacy of ribociclib + letrozole (+ goserelin or leuprolide) in Full Analysis Set.

The following endpoints as defined by RECIST1.1 will be use key secondary objectives:

- Time-to-Progression (TTP) based on investigators' assessment
- Overall response rate (ORR) for patients with measurable disease
- Clinical Benefit Rate (CBR) (including patients with CR, PR, SD/NCRNPD>24 weeks)

Time to progression (TTP) is defined as time from date of start of treatment to the date of event defined as the first documented progression or death due to underlying cancer (Appendix 14.3: Novartis RECIST Guideline v 3.2). Patients with symptoms of rapidly progressing disease without radiologic evidence will be classified as progression only when clear evidence of clinical deterioration is documented and/or patient discontinued due to 'Disease progression' or death due to study indication. When there is no documentation of radiologic evidence of progression, and the patient discontinued for 'Disease progression' due to documented clinical deterioration of disease, the date of discontinuation is used as date of progression.

Overall response rate (ORR) is defined as the proportion of patients with best overall response of complete response (CR) or partial response (PR) according to RECIST 1.1.

Clinical benefit rate (CBR) is defined as the proportion of patients with a best overall response of complete response (CR), or partial response (PR) or an overall lesion response of stable disease (SD), lasting as per local review, for a duration of at least 24 weeks. CR, PR and SD are defined according to RECIST 1.1 (see Appendix 14.3 for details)

The distribution of TTP will be estimated using the Kaplan-Meier method. The median TTP along with 95% confidence intervals will be presented. Proportions of patients with ORR and CBR as assessed by investigator will be calculated and presented along with the approximate 95% confidence intervals using Clopper and Pearson (1934) exact method.

In addition, PRO will be assessed using FACT-B instrument (See Section 10.5.4).

During Extension Phase, frequency of AEs & SAEs will be summarized.

The proportion of patients with clinical benefit as assessed by investigator will be reported at each scheduled visit during Extension Phase.

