#### 2.2.6 Subgroup of interest

The following subgroups of interest may be used at interim and/or final analysis:

- Region (Latin American, Region Europe, Asia)
- Country (countries with at least 100 patients including, but not limited to US, Canada, Italy, Spain, France, Belgium, Czech Republic)
- Prior treatments for advanced disease (no treatments vs. chemotherapy)

Novartis	Confidential	Page 19
SAP	22-Feb-2022 (1:27)	CLEE011A2404

- Prior treatments for (neo)adjuvant (no treatments, endocrine only, chemotherapy only, both endocrine and chemotherapy )
- ECOG PS (PS 0-1 and 2)
- Liver involvement (yes vs. no)
- Lung involvement (yes vs. no)
- Lung or liver involvement (yes vs. no)
- Bone lesion only metastasis
- Other visceral/soft tissue involvement (adrenal, kidney, lymphonodes/soft tissue, etc.)
- Number of metastatic sites  $(0, 1, 2, \ge 3)$
- Age (<65, 65-<70, 70-<75, ≥75 years)
- Gender (male and female)
- Race (Asian vs. Non-Asian)
- Hormonal status at baseline (premenopausal vs. postmenopausal)

The objectives for carrying out analyses on these subgroups are to describe/characterize the treatment effect in these subgroups, to identify potential safety issues that may be limited to a subgroup of patients, or safety issues that are more commonly observed in a subgroup of patients.

With exception of male, summary tables will only be performed if at least 100 patients are present in each subgroup.

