## 2.7.1 Secondary endpoints

## Time to progression (TTP)

Time to progression is defined as time from date of start of treatment to the date of event defined as the first documented progression or death due to underlying cancer (Novartis RECIST Guideline v 3.2). Patients with symptoms of rapidly progressing disease without radiologic evidence will be classified as progression only when clear evidence of clinical deterioration is documented and/or patient discontinued due to 'Disease progression' or death due to study indication. When there is no documentation of radiologic evidence of progression, and the patient discontinued for 'Disease progression' due to documented clinical deterioration of disease, the date of discontinuation is used as date of progression.

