## Overall response rate (ORR)

Overall response rate is defined as the proportion of patients with best overall response (BOR) of complete response (CR) or partial response (PR) according to RECIST 1.1 (see Appendix 3 of the study protocol). ORR will be calculated based on the FAS in patients with measurable disease at baseline using local investigators review of tumor assessment data. Tumor assessments performed before the start of any further antineoplastic therapy (i.e. any additional secondary antineoplastic therapy or surgery) will be considered in the assessment of BOR.

Palliative radiotherapy is allowed as per protocol. If palliative radiotherapy is initiated after the start of study treatment, the reason for its use must be clearly documented and progression as per RECIST 1.1 must be ruled out. For example, palliative radiotherapy given in the trial for analgesic purposes or for lytic lesions at risk of fracture will not be considered as cancer therapy for the assessment of BOR analyses.

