## Analysis of AESIs

An adverse event of special interest is a grouping of adverse events that are of scientific and medical concern specific to compound ribociclib. These groupings are defined using MedDRA terms, SMQs (standardized MedDRA queries), HGLTs (high level group terms), HLT (high level terms) and PTs (preferred terms). Customized SMQs (Novartis MedDRA queries, NMQ) may also be used. A NMQ is a customized group of search terms which defines a medical concept for which there is no official SMQ available or the available SMQ does not completely fit the need. It may include a combination of single terms and/or an existing SMQ, narrow or broad. For each specified AESI, number and percentage of patients with at least one event of the AESI occurring during on treatment period will be summarized.

Summaries of these AESIs will be provided, (specifying grade, SAE, relationship, leading to treatment discontinuation, leading to dose adjustment/interruption, hospitalization, death etc.). If sufficient number of events occurred, analysis of time to first occurrence will be applied.

A listing of all grouping levels down to the MedDRA preferred terms used to define each AESI will be generated.

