# 4 Change to protocol specified analyses

No change from protocol specified analysis was made.

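### SAP 2.7.2 shows the median TTP only if there are enough tumour responses, which are not TTP events; the protocol sets no such condition

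*SAP*

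**What the plan says.** Protocol 10.5.1 is unconditional: "The median TTP along with 95% confidence intervals will be presented". SAP 2.7.2 (TTP) keeps the Kaplan-Meier method and names the Brookmeyer-Crowley interval, but presents the median and CI "only if a sufficient number of responses are observed". It gives no number for sufficient. The next sentences of that paragraph plan a plot, the 25th and 75th percentiles and Kaplan-Meier probabilities from 3 to 30 months, none with a condition.

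SAP 2.7.1 defines the TTP event as "the first documented progression or death due to underlying cancer". It defines a response as a best overall response of CR or PR, and for the response rate "ORR will be calculated based on the FAS in patients with measurable disease at baseline".

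Three other places in the SAP bear on this:
- Section 5.4 obtains the Kaplan-Meier median and its 95% CI without a condition.
- Section 2.8.2, for adverse events of special interest, ties a different time-to-event analysis to events: "If sufficient number of events occurred, analysis of time to first occurrence will be applied".
- Section 4 declares: "No change from protocol specified analysis was made".

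**The concern.** The display rule for the main TTP statistic names a quantity that plays no part in estimating it. Because no threshold is given, whether the median appears would be settled after the data are seen, on a count of CR and PR. The rule can err both ways: a group with many progressions and few responses could lose an estimable median, and a group with many responses and few progressions would satisfy the rule without having a median to show. The SAP also departs here from the protocol and from its own section 5.4 while stating that nothing was changed. At stake is consistent reporting of a secondary efficacy endpoint, chiefly in subgroups.

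**Working it through.** The documents attach no figure to the condition, so there is no stated number to reproduce. The check is a comparison of rules, followed by a rough count of responses.

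**1. What fixes the median.** The Kaplan-Meier estimate is S(t) = product over event times of (1 - d/n), where d is the number of TTP events and n the number at risk. The median is the first t at which S(t) is 0.5 or below. Only progressions, cancer deaths and censoring enter; CR and PR do not.

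**2. The rules side by side.**

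| Place | Statistic | Condition |
|---|---|---|
| Protocol 10.5.1 | Median TTP, 95% CI | None |
| SAP 2.7.2 | Median TTP, 95% CI | Enough responses |
| SAP 2.7.2 | Quartiles, KM probabilities | None |
| SAP 5.4 | KM median, 95% CI | None |
| SAP 2.8.2 | Time to first AESI | Enough events |

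**3. Full analysis set.** The inputs come from the pivotal trial's ribociclib arm (protocol 1.1.1 and 1.2.1.2.2): response rate 40.7% at the first analysis and 42.5% at the update; 24-month PFS 54.7%.
- Responses in 3,000 patients: 3,000 x 0.407 = 1,221 and 3,000 x 0.425 = 1,275.
- Events by 24 months: 3,000 x (1 - 0.547) = 1,359. This assumes the pivotal PFS rate and 24 months of follow-up for everyone. TTP events would be somewhat fewer, because TTP leaves out deaths from other causes.

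Any plausible threshold on either count would be met overall.

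**4. Patients with non-measurable disease only.** Protocol Table 14-6 gives them CR, non-CR/non-PD, unknown or PD, with no PR category. Section 14.3.27 nevertheless recommends including them in endpoints that depend on progression. The updated pivotal figures indicate how rare responses are in this group. Denominators follow from the CIs by n = 1.96² p(1 - p)/h², with h the half-width:
- All patients, 42.5% (37.2 to 47.8), h = 0.053: n = 334, which equals 668/2 (1:1 allocation assumed). Responders: 0.425 x 334 = 142.
- Measurable disease, 54.5% (48.4 to 60.6), h = 0.061: n = 256. Responders: 0.545 x 256 = 139.5, about 140.
- Remainder: about 2 to 3 responders among 334 - 256 = 78 patients, roughly 3%.

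The first analysis, handled in the same way, leaves about 1 in 77, roughly 1%. These are small differences between large rounded numbers. Rounding of the limits puts the measurable denominator between 251.9 and 260.3; with 334 fixed, the remainder then runs from 142 - 0.545 x 260.3, about 0, to 142 - 0.545 x 251.9, about 5.

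At 1% to 3%, a group of 100 such patients (the SAP's minimum size for subgroup tables) would yield 1 to 3 responses, and the binomial chance of 10 or more is below 0.001. The documents give no progression rate for this group, so whether its median would be reached is unknown. The response count does not settle that either way.

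**5. The reverse error.** In the pivotal arm, 42.5% responded, yet PFS at 24 months was still 54.7%, above one half. A similar group with data only to 24 months would have many responses and no median.

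**The case against.** The strongest reply is that this is one wrong word. SAP 2.8.2 uses the same kind of hedge with the right noun, and SAP 5.4 states the median without any hedge, so the author almost certainly meant events. With expected median follow-up of about 24 months against a reference median PFS of 25.3 months, some caution about estimability is reasonable. The overall median is not at risk. The study is single-arm and tests no hypothesis, and the curve is plotted anyway, so a reader could take the median from it. All of this stands, and it limits the weight of the point. It does not remove it: this sentence is the operative rule for TTP, and even with the noun corrected it would leave an unquantified condition that the protocol does not contain.

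A reader might go further and infer that the median would be suppressed in bone-only disease, which SAP 2.2.6 lists as "Bone lesion only metastasis". The documents do not support that:
- Subgroup analyses are optional in both documents, and neither commits to TTP by subgroup.
- Bone-only is not the same as non-measurable. Protocol 14.3.4 lets lytic or mixed lesions with a measurable soft-tissue component count as measurable. Measurability itself is not a listed subgroup.
- Patients with non-measurable disease can still achieve CR.
- No bone-only share, response rate or event rate is given, so any projected count of bone-only events would rest on assumption alone.
- Without a threshold, withholding is possible but cannot be predicted.

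**Conclusion.** The condition is wrong as written and conflicts with protocol 10.5.1 and SAP 5.4, and SAP section 4 does not declare it. That conclusion rests on the text alone. It is also incoherent to report the 25th and 75th percentiles freely while restricting the 50th. The practical size is minor. The overall median should appear in any case, given more than 1,000 expected responses; this assumes that the pivotal trial's response rates carry over roughly to this broader population. The remaining exposure is to low-response groups, if TTP is tabulated in them, and to groups that meet the rule without reaching a median. Nothing in the documents shows that responses were chosen in order to report selectively.

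**What to change.** In SAP 2.7.2, delete the conditional phrase. State that the median TTP and its Brookmeyer-Crowley 95% CI are presented for the full analysis set and for any subgroup in which TTP is tabulated. Show the median or a confidence limit as not estimable where it is not reached, and give the numbers of events and at risk alongside. This brings 2.7.2 into line with protocol 10.5.1 and SAP 5.4 and makes the statement in SAP section 4 true on this point. The cost is one sentence of SAP wording; some subgroup medians may print as not estimable. No new data are needed.
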